11.3 Secondary Efficacy Endpoint Subgroup and Sensitivity Analyses

Secondary efficacy endpoints will be subject to the same sensitivity and subgroup analyses as the primary efficacy endpoints.

The following laboratory parameters will be collected and analyzed by a central laboratory. Change from baseline to both Day 8 or discharge will be summarized for inflammatory biomarkers (IL-6, hsCRP) and coagulation biomarkers (PT, PTT, factor Xa and tissue factor). All data will be listed. Analyses will be by generalized linear mixed effects models as described above for sensitivity and subgroup in the primary efficacy endpoint. For purposes of interpretation of outcomes, IL-6 and hsCRP are considered measures of systemic inflammation, PT, PTT and factor Xa are coagulation parameters, and tissue factor is the biologic target of rNAPc2. In addition, in a subset of participants anti-phospholipid antibodies known to be generated in COVID-19 and inhibited by rNAPc2, are being measured at baseline, Day 8/discharge and on Day 30 at a specialty laboratory.

11.4 Additional Safety Analyses

Decrease in hemoglobin level reported by local laboratories will be monitored to be used as an indicator of potential bleeding risk. As a variable, decrease will be dichotomized such that a decrease of more than 3 g/dL will constitute an event, and any decrease of less than 3g/dL will constitute a non-event. To provide the broadest view of potential bleeding risk, heparin treated subjects will be considered together regardless of prophylactic or therapeutic regimens. The rNAPc2 subjects will be stratified with regard to regimen received. A Cochran Mantel Haenszel Test with stratification will be performed to examine the frequency of events and non-events across the two treatment groups.

12 Changes from Methods Planned in the Protocol

Wilcoxon Signed Rank will not be used in the analysis of the primary efficacy endpoint.

Probability of discharge as assessed by ACTT ≥ 6 by Day 8 and Day 30 post randomization is now a secondary efficacy endpoint.

Composite of death, thrombosis, organ support, or rehospitalization within 30 days is now a secondary efficacy endpoint.

Rehospitalizations and their relatedness to COVID-19 will be adjudicated.

13 References

14 Appendix

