8.3 SAFETY AND OTHER ASSESSMENTS

Safety assessments will include monitoring of serious and non-serious AEs and study endpoints. Efficacy and safety endpoints, including all bleeding events, will not be considered as AEs or SAEs (see [Section 8.4 Adverse Events and Serious Adverse Events](#)). Safety evaluations will be assessed by the investigator per the SoA via EMR review, telephone or web contact with the participant or their health care provider.

Safety Events:

Bleeding events are considered safety endpoints for the study.

The study will classify bleeding events as major, non-major clinically relevant or non-major non-clinically relevant. Safety endpoints for this study include major, critical site and fatal bleeding and non-major clinically relevant bleeding using modified International Society on Thrombosis and Haemostasis (ISTH) bleeding criteria. All bleeding events will be assessed, classified and reported by the investigator in the eCRF. Major bleeding events will be adjudicated by the CEC.

An ISTH major bleeding event is defined as overt bleeding that is associated with:

- A fall in hemoglobin of 2 g/dL (1.24 mmol/L) or more, or
- A transfusion of 2 or more units of packed red blood cells or whole blood, or
- A critical site: intracranial, intraspinal, intraocular, pericardial, intra-articular, intramuscular with compartment syndrome, retroperitoneal, or
- A fatal outcome.

Non-major clinically relevant bleeding is defined as overt bleeding not meeting the criteria for major bleeding but associated with medical intervention, unscheduled visit or telephone call with a healthcare provider or temporary or permanent cessation of study treatment or associated with discomfort for the participant such as pain or impairment of activities of daily life.

Bleeding events not meeting the definition of major or non-major clinically relevant bleeding will be classified as non-major, non-clinically relevant.

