9.4.4 SAFETY ANALYSES

Incidence rates of AEs including adjudicated bleeding events, all, serious, fatal, severe and treatment-related AEs reported throughout the conduct of the study will be tabulated by preferred term and system organ class.

Changes in laboratory values and vital signs will be summarized with descriptive statistics. The incidence of concomitant medications will also be summarized.

Drop in hemoglobin level as reported per local laboratory data will be used as an indicator of potential bleeding risk.

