8.1 Primary Safety Endpoint

The primary safety endpoint is major or non-major clinically relevant bleeding through the earliest of Day 8 or two days after Day of Discharge if prior to Day 8.

The frequency and percentage of participants with major or non-major clinically relevant bleeding within 8 days of randomization as adjudicated by the CEC will be presented by each rNAPc2 dose and any heparin dose.

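### SAP 11.4 leaves a hemoglobin fall of exactly 3.0 g/dL unclassified and, without a stated reason, codes falls of 2 to <3 g/dL as non-events

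*SAP*

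**What the plan says.** Protocol 9.4.4 plans a hemoglobin analysis without a cut-off: "Drop in hemoglobin level as reported per local laboratory data will be used as an indicator of potential bleeding risk". SAP 11.4 repeats the purpose ("Decrease in hemoglobin level reported by local laboratories will be monitored to be used as an indicator of potential bleeding risk") and supplies the rule: "a decrease of more than 3 g/dL will constitute an event, and any decrease of less than 3g/dL will constitute a non-event". It pools the heparin regimens so as to view potential bleeding risk as broadly as possible, and separates the rNAPc2 regimens. The test follows: "A Cochran Mantel Haenszel Test with stratification will be performed to examine the frequency of events and non-events across the two treatment groups".

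Protocol 8.3 defines the major-bleed endpoint. The lead-in is "An ISTH major bleeding event is defined as overt bleeding that is associated with", followed by four alternative criteria, of which the first is "A fall in hemoglobin of 2 g/dL (1.24 mmol/L) or more, or". The other three are transfusion of two or more units, a critical site, and a fatal outcome.

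The primary safety endpoint is a separate analysis. SAP 8.1 reports "major or non-major clinically relevant bleeding within 8 days of randomization as adjudicated by the CEC", and SAP 8.2.1 does the same through Day 30. Neither refers to the 3 g/dL cut.

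**The concern.** Two things are wrong with the dichotomy.

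First, it has a hole. One half of the rule is strictly above 3 g/dL and the other strictly below, so the value 3.0 has no category. Hemoglobin is a rounded laboratory value, so exact 3.0 g/dL falls can occur. The programmer would have to choose event, non-event or missing, possibly with treatment codes in view.

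Second, the cut is stricter than the hemoglobin component of the trial's own major-bleed definition. Falls of 2 to <3 g/dL are grouped with no fall at all. That sits poorly with the stated aim of a broad view, and the SAP gives no reason for it.

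At stake is how much this supportive analysis can tell the reader. Finding a regimen with an acceptable bleeding profile is a primary Phase 2b objective. Each rNAPc2 arm has about 40 patients (160 randomized 1:1:2). If few patients exceed 3 g/dL, the comparison will say little about either regimen, and the SAP plans no hemoglobin analysis at a lower cut.

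**Working it through.** The documents give no sample size, power or event rate for this analysis, so there is no planned figure to reproduce.

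**Step 1: apply both rules to every possible fall.** Inputs: event if fall > 3 and non-event if fall < 3 (SAP 11.4); hemoglobin component met if fall ≥ 2 (Protocol 8.3). Assumption: values are reported to 0.1 g/dL, which the documents do not state. Falls from 0.0 to 6.0 g/dL were classified in steps of 0.1.

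| Fall (g/dL) | SAP 11.4 | Hemoglobin component of Protocol 8.3 |
|---|---|---|
| 0.0-1.9 | non-event | not met |
| 2.0-2.9 (10 values) | non-event | met |
| 3.0 (1 value) | neither | met |
| 3.1-6.0 | event | met |

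Making the cut inclusive at 3 g/dL removes the unassigned value but leaves the 10 values from 2.0 to 2.9 as non-events. A cut at ≥2 versus <2 g/dL leaves no unassigned value and no disagreement with Protocol 8.3.

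**Step 2: illustrate the size.** The documents give no hemoglobin distribution, so the means and SDs below are assumptions. Let the largest fall per patient be normal with mean m and SD s. With rounding to 0.1 g/dL:

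- P(≥2) = 1 − Φ((1.95 − m)/s)
- P(>3) = 1 − Φ((3.05 − m)/s)
- P(exactly 3.0) = Φ((3.05 − m)/s) − Φ((2.95 − m)/s)

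For m = 0.8 and s = 1.2: (1.95 − 0.8)/1.2 = 0.958, giving 16.9%; (3.05 − 0.8)/1.2 = 1.875, giving 3.0%; (2.95 − 0.8)/1.2 = 1.792, giving 0.6% at exactly 3.0.

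| Assumed mean, SD (g/dL) | ≥2 | >3 | exactly 3.0 | ≥2, per 40 patients | >3, per 40 patients |
|---|---|---|---|---|---|
| 0.5, 1.0 | 7.4% | 0.5% | 0.18% | 2.9 | 0.2 |
| 0.8, 1.2 | 16.9% | 3.0% | 0.62% | 6.8 | 1.2 |
| 1.0, 1.3 | 23.2% | 5.7% | 0.94% | 9.3 | 2.3 |

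The counts are the unrounded percentages times 40, the approximate size of one rNAPc2 arm, and assume that every patient has usable serial local values. In the 80 pooled rNAPc2 patients, 0.1 to 0.8 would fall at exactly 3.0 g/dL (80 × 0.18% to 80 × 0.94%).

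Only the direction is free of assumptions: every fall above 3 g/dL is also a fall of at least 2 g/dL.

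**The case against.** The strongest reply is that the two cuts measure different things. In Protocol 8.3 the hemoglobin fall counts only when bleeding is overt. SAP 11.4 takes a laboratory fall with no such condition, and falls of 2 g/dL can come from dilution or phlebotomy. A higher cut for an unconditioned measure is a defensible gain in specificity. This stands as a reason not to replace 3 with 2 outright. It does not explain why the SAP gives no rationale, and it does not close the gap at 3.0.

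Four stronger readings are tempting, and the documents do not support them.

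- **That bleeds are lost.** An overt bleed with a 2.5 g/dL fall still meets Protocol 8.3 and counts in the adjudicated primary and Day 30 endpoints. Conversely, a 2.5 g/dL fall without overt bleeding is not a major bleed.
- **That SAP 12 omits a departure from the protocol.** Protocol 9.4.4 gives no cut-off, and Protocol 9.4.1 leaves analysis detail to the SAP. Setting a threshold fills in detail.
- **That hemoglobin is the one bleeding measure independent of the unblinded site.** These are local values, recorded when the hospital happens to test, plus extra values judged to show a clinically significant change. The site knows the assignment. Bleeds, for their part, are adjudicated by a blinded CEC, although sites still identify and report them.
- **That the analysis is charged with detecting under-reporting or drives dose choice.** No section says so. The cross-tabulation proposed below would be an added use of the data.

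It is also fair to say that the gap at 3.0 is a drafting slip that would touch less than one patient in 80 on the illustrative figures.

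**Conclusion.** The point holds as a defect in a supportive safety analysis. Two facts follow from the text alone: a fall of exactly 3.0 g/dL is unassigned, and falls of 2 to <3 g/dL meet the hemoglobin component of the major-bleed definition yet are coded non-events without a stated reason. The primary safety endpoint and the Day 30 bleeding endpoint are unaffected.

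The number of patients concerned cannot be computed from the documents. The 7-23% versus 0.5-6% comparison rests on assumed normal distributions and 0.1 g/dL reporting. It shows that the choice of cut could matter a good deal to the event count; it does not predict that count. Whether 2 or 3 g/dL is the better single cut is a trade-off between sensitivity and specificity, which the documents do not settle. Reporting both avoids the choice.

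**What to change.** In SAP 11.4:

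1. Close the boundary: a fall of ≥3 g/dL is an event and a fall of <3 g/dL is a non-event.
2. Add a second dichotomy at ≥2 versus <2 g/dL, matching the hemoglobin component in Protocol 8.3, with the same comparison across arms.
3. Cross-tabulate falls of ≥2 g/dL against reported major bleeds, by arm.

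The cost is a wording change, one further table row and one small cross-tabulation. Local hemoglobin is already collected under Protocol 8.1.2. The downside is that the ≥2 g/dL cut is less specific. The retained ≥3 g/dL row lets the reader see how far the result depends on the cut.

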14.1 COVID Severity Definitions

Subgroup analyses according to baseline severity of COVID-19 illness will be performed. The primary categorization will be adapted from the WHO Scale for Clinical Improvement (mild vs. severe) from the COVID-19 Therapeutic Trial Synopsis (see below). In addition, patients may be categorized according to critical illness at baseline (based on use of inotropes or vasopressors, intubation, CPAP/BiPAP, Venturi, and non-rebreather oxygen supplementation) as well as the combination of both approaches, further subgrouping the WHO Hospitalized Severe into those with and without critical illness at baseline.

Severity	Definition
Hospitalized Mild	No oxygen therapy
Hospitalized Mild	Oxygen by mask or nasal prongs
Hospitalized Severe	Non-invasive ventilation (inc. high-flow O2)
Hospitalized Severe	Intubation and mechanical ventilation
Hospitalized Severe	Ventilation and additional organ support (vasopressors, renal replacement therapy, ECMO)

14.2 Descriptions of the Models and Methods Used

14.2.1 Bayesian Description

14.2.2 MI Description

14.2.3 Power Description
